revisit the setting of the intervention may bias responses. We will test this by conducting a methodological experiment, where half of the groups will be asked to complete follow-up data online in a place and time of their own choosing (within a data collection window set by the research team) and half are invited to revisit the club at a set time/date to complete follow-up data online then and there. For the former group, completion of measurements will be closely monitored, and reminders sent via email, text and follow-up phone calls, if necessary; for the latter group, non-attendees will be forwarded the online link and will again receive reminders (RQ12).

For all participants, if online accessibility is an issue, a paper version of the questionnaire will be sent/used, if necessary. For those receiving the intervention, and where they have agreed, push notifications to complete the follow-up data can be sent from the smartphone app. Given the age profile of participants (18-44) we anticipate that most will have internet access and will complete the surveys online. Where neither online nor paper-based responses are received, a member of the research team will call participants and attempt to collect the data over the phone.

Data and statistical analysis: Statistical analysis of the pilot RCT data will be undertaken by the RCB. In order to address RQ11 (best outcome measures) and RQ10 (the potential of FFAB to effect change), a full detailed statistical analysis plan will be developed and agreed prior to database lock and unblinding of the statistician. Descriptive summaries of the pilot RCT outcomes, including the numbers invited to participate, the numbers and proportions recruited, and retained during the study (six months post-baseline), and at the primary follow-up time-point (12 months post-baseline) will be provided along with 95% confidence intervals. The completeness of the proposed efficacy outcome measures at each of the four data collection time points during the study, will be provided. The distribution of the data will be explored and the variation, both between clubs and between participants, will be assessed. Baseline factors and their association with outcomes will also be examined. The intervention effect on outcome measures at our primary follow-up time point (12 months post-baseline) will be estimated in exploratory analyses and reported with corresponding 95% confidence intervals, as well as the intervention effect within each club. Changes in continuous outcome measures at each follow-up time point may be analysed using parametric or non-parametric models, depending on the nature of the data (eg. Normal regression, Poisson regression, Negative-Binomial regression, etc.). If required, appropriate transformations of the data will be made prior to analysis (eg. log transformation, square root, etc.). Categorical outcome measures at each follow-up time point (including dichotomised continuous outcome measures if required) will be analysed using appropriate regression techniques depending on the nature of the data (eg. binary logistic regression, ordinal regression, etc.). In each model, baseline values of the outcome measure will be adjusted for where available and the stratification variables will be accounted for accordingly. These models may then be extended to explore repeated measures analyses using data recorded during the study. We can also explore, recognizing the limits of power, whether it would be of benefit to adjust for other data collected at baseline. Based on these findings, and analyses of qualitative interviews and focus group data, we will refine our theory of change and logic model (RQ15).

Health economic evaluation: This pilot study is the first attempt to assess the feasibility of conducting the economic evaluation of an intervention directed towards reducing gambling behaviour. Furthermore, this is the first study of this type in the UK. In view of the novelty of the analysis, the economic evaluation alongside the FFAB feasibility trial represents a unique opportunity to explore the anticipated complexity associated to the identification, measurement and valuation of the plethora of inter-sectoral costs and outcomes associated to gambling.

Addressing RQ14, the economic evaluation alongside the FFAB feasibility trial will: identify the relevant costs and consequences associated to gambling; define and refine economic data collection methods; test the feasibility of data collection instruments in capturing participants' short term use of health and community services (RQ14); assess relevant short-term outcome measurement tools [45].

An economic conceptual model [8] will be developed to: systematically identify and represent all relevant multi-sectoral outcomes and costs (cost savings) associated to the intervention over the short and long term; highlighting the complex causal pathways and the multiple layers (i.e. individual; family; community; society) where cost and consequences of gambling arise; identify relevant pre-existing comorbidities/conditions which may led to spurious correlation between the intervention and its associated costs and outcomes. In line with current guidance [46], bespoke data collection instruments will capture the full range of inter-sectoral costs and consequences associated to gambling behaviour. adopting a wide public sector perspective. We will test the feasibility to capture use of health services (visits to the GP; usage of mental health services etc.); use of community services (e.g. community and social services, such as support groups); impacts on income and productivity (e.g. pre-absenteeism).

The feasibility of using resource use logs to capture the costs to deliver the intervention (i.e. cost of coaches and experts in gambling harm; participants' opportunity costs; cost of the venue) will also be assessed. Suitable reference costs (e.g. PSSRU [47]) will be identified. The preference-based instruments, ICECAP-A and EQ-5D-5L [38, 39], will be used to assess short-term health-related QoL and capability wellbeing, and validated against potential primary and secondary outcomes (e.g., self-reported gambling frequency; total money spent on gambling; self-esteem and mental health).

Descriptive statistics for each outcome and cost variable will be reported, for each data collection time point, alongside means, standard deviations and bootstrapped 95% confidence intervals by intervention/control group. An exploratory cost-consequences analysis (CCA), as recommended by the NICE public health economic evaluation guidance [48], will be conducted - reporting costs alongside consequences (such as QALYs, measures of gambling frequency; money spent on gambling; mental wellbeing) for intervention and control groups. Key sources of uncertainty in relation to the probability of the intervention being cost-effective will also be explored

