The FFAB intervention will also use engagement in group-based physical activities (PA) within the social setting of the football club to foster a socially supportive network of men. Unlike FFIT, where improvement in PA was an important secondary outcome, PA in the FFAB programme has a very different role. It is used primarily as a mechanism to strengthen social networks and peer support, and as a form of behavioural substitution by providing a displacement activity for gambling that men can focus on and bond around between sessions. To help to encourage this feature, the smartphone app is designed to allow participants to record and monitor their step counts, drawing on learning about the importance and enjoyment of this type of self-monitoring [31]. This feature will also encourage more general engagement with the app itself as a form of self-monitoring as well as goal setting, both of which are important in the generation of autonomy. It will allow participants to track the amounts of time and money they spend on gambling on a daily basis, which can be used in weekly group feedback sessions in which men set their own spending goals.

Our logic model incorporates core elements to test SDT as a provisional theory of change; but also includes other elements to explore complementary perspectives including maintenance processes, and IMB, which have also been used to understand gambling behaviour [32, 33] (see Figures 2&3). In this way, if successful, our feasibility study will afford the material required to develop a fully-specified model of change in a subsequent large-scale RCT of FFAB.

Figure 2: Logic Model for FFAB						
laurita	Activities			Outcomes		
Inputs	Attracting men	Engaging men	Initiating change	Maintaining change	Short term	Long term

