 Data on the acceptability of FFAB delivery by coaches collected by i) focus groups with with feasibility coaches after the full delivery of FFAB to produce thematic insight into: the confidence of the coaches to deliver FFAB; what worked and what did not; challenges and how to over come these and revisions to coach training and the FFAB programme and ii) team observation of each session of FFAB in phase. Team observations will generate field notes identifying key themes for discussion by the full FFAB team in revising the programme.

Other outcomes from this phase will be further refinement of the FFAB intervention manual and coaches delivery manual, based on the feedback given above and finalisation of the recruitment and retention strategy.

Phase 3:

The broad outcome of the pilot trial is to assess the potential effectiveness of FFAB in improving wellbeing by reducing gambling involvement (RQ10). We propose to test the responsiveness of **potential primary outcomes** in the pilot trial: investigating both measures of improvements in health and wellbeing and of reductions in gambling involvement.

For health and wellbeing, the WEMWBS and ONS four item wellbeing questionnaire will be used. Data from the Health Survey for England and the British Gambling Prevalence Survey 2010 show that gambling behaviour is associated with both: problem gamblers are more likely to have lower WEMWBS and ONS scores [2,36]. WEMWBS has been shown to be sensitive to change in evaluations of diverse public health interventions and programmes including general lifestyle interventions and parenting programmes [37]. The ONS wellbeing questions cover personal wellbeing ranging from happiness to life satisfaction and have been developed to National Statistics standards. We will also include measures of health-related quality of life and capability suitable for use in economic evaluation, i.e. EQ-5DL and ICECAP-A [38,39].

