Gambling involvement will be measured on two domains: breadth and depth [36, 40] and will be captured using validated measures of gambling involvement: number of different types of gambling activities undertaken (breadth) and self-reported gambling frequency (total number of bets placed, number of days spent gambling); total money spent on gambling; and total time spent on gambling (depth). All of these questions were developed and tested for the British Gambling Prevalence Survey 2010 [36]. Their validity and reliability have been assessed, showing good to excellent reliability and validity [41] when compared with diary methods.

Proposed **secondary outcome measures** include specific items from the DSM-5 problem gambling screening instrument pertinent to our intervention (such as betting more than one could afford to lose, trying and failing to cut back on gambling, gambling as escapism and being restless or irritable when trying to cut back on gambling) [42]; a measure of social support, (an adapted version of the Shortened Social Support Scale

made appropriate for gambling and perceived social support more generally) [43]; and Rosenberg's Self Esteem Scale [44].

We will collect information on attendance and logged data of app diary usage. If data quality permits, we will use data from the app to help inform progress towards reductions in gambling involvement (RQs7,12). Analysis of app data will be done post-intervention. We will conduct focus groups with intervention participants after they have completed the intervention to understand their experiences of FFAB, of making and sustaining reduction in their gambling behaviours, and of the research procedures (RQs8&10). Post intervention, we will conduct exit interviews with non-completers, and interviews with coaches and football club representatives to understand their views and experiences of delivering FFAB and of involvement in the pilot (RQs5,6,8,9).

5 STUDY DESIGN and METHODS of DATA COLLECTION AND DATA ANALYIS

The research design is a mixed methods feasibility study and pilot multi-site parallel group RCT. It comprises three phases, corresponding to our three main research objectives.

Phase 1. Refinement of FFAB for initial delivery (months 0-6)

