Intervention: FFAB is a 9-week, face-to-face group-based programme that aims to engage men in reducing their gambling involvement. FFAB is delivered by fully trained community coaches at professional football club home stadia. Each session lasts 90 minutes and includes 'classroom-based' education around gambling behaviour, motivations and impacts, followed by group-based physical activity sessions. The classroom sessions will support men to: understand the role, extent and influences on gambling in their life (including other people and environmental and psychological triggers); understand and reassess dysfunctional beliefs (e.g. around risk taking and chance); develop strategies to avoid triggers for gambling and relapse ('if-then' plans); identify the benefits to them and other people in their lives of reducing their gambling; and identify ways that they personally can (re)gain control (autonomy) over their gambling behaviours. Each session will be designed to be highly interactive, using whole group discussions, games and small group working, to allow men to support each other to practice and build skills (competence) in order to monitor and reduce the amount of money and time they spend gambling. Interaction between men will be encouraged to promote a team spirit and facilitate discussion of sensitive issues. In the group-based physical activity sessions that follow, men will be given the opportunity to take part in football-based activities (including training drills, walking football and small-sided matches) using club facilities. These are intended as a means to foster social

connectedness and male bonding around a substitution activity that is specifically nongambling related. This is part of our goal to encourage a shift in shared values and attitudes around the idea of 'reclaiming the game'.

During sessions, men will learn to use the smartphone app to record time and money spent gambling, and to set SMART goals around these behaviours. Men will also be able to use the app to monitor and record their daily physical activity (step counts). It is anticipated that this functionality will encourage men's engagement with the app, and, by extension, with the gambling diary functionality. Discussion around app-based recording of PA is also intended to encourage bonding within the group as a subtle means of leading into potentially more sensitive discussions around recording of time and money spent gambling.

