Control/Comparison group: Following baseline data collection, participants in the control arm will continue with their daily routines and usual activities.

Assessment and follow-up: We have four stages of assessment and follow-up for all participants: the first is baseline data collection, when information relating to all outcome measures (the outcome questionnaire) is collected prior to randomisation to the intervention and control groups. The second is immediately after the intervention group have completed FFAB (10 weeks post-baseline). This will allow us to explore any immediate effects of the intervention. The third is at six months post-baseline, to assess impact across a longer time frame. Finally, the outcome questionnaire will be repeated at 12 months post-baseline to give insight into the sustainability of potential impact (RQ10). This will be our primary data collection point for our RCT outcome measures and will be used to assess progression.

Methods for data collection: To maximise attendance at baseline and retention for follow-up, baseline data collection will take place in club stadia, a strategy successfully employed in the FFIT and EuroFIT RCTs. The baseline measurement session at the club, conducted prior to randomisation, will be used to explain more about the study, and its purpose and context, and a club coach will be on hand to answer questions about the programme.

An electronic case report form (eCRF) will be used to collect study data. This system will be developed by the Robertson Centre for Biostatistics (RCB – the Data Centre and Biostatistics arm of the UKCRC fully registered Glasgow Clinical Trials Unit) based within the University of Glasgow. Baseline and follow-up data will be collected using the eCRF and managed by the RCB. This will be a confidential, self-completion method, which is optimal for collecting data on sensitive behaviours. Individual participant user accounts will be provided to each participant for them to log in and enter their baseline and follow-up data.

FFAB's outcome data is completely self-reported, therefore it may not be necessary for participants to revisit the club for follow-up data collection, as they could do this confidentially from their own home. However, it may be the case that revisiting the club could be positive in terms of retention. Yet there is also a risk that asking participants to

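### Self-reported money, time and possibly days gambled may be measured differently by arm at follow-up, because only intervention men are described as having a daily app diary and use of records is neither standardised nor recorded

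*Protocol*

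**What the plan says.** Section 4.2 of the Protocol says that Phase 3 tests the responsiveness of potential primary outcomes, "investigating both measures of improvements in health and wellbeing and of reductions in gambling involvement". The depth measures of gambling involvement include "number of days spent gambling); total money spent on gambling; and total time spent on gambling (depth". The same section supports these questions as "showing good to excellent reliability and validity [41] when compared with diary methods", without giving an agreement figure. Section 5 (Phase 3, Methods for data collection) states that "FFAB's outcome data is completely self-reported".

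The intervention includes a tool that records two of these quantities. In the sessions "men will learn to use the smartphone app to record time and money spent gambling, and to set SMART goals around these behaviours". Section 3 says of the app: "It will allow participants to track the amounts of time and money they spend on gambling on a daily basis". Section 5 (Phase 1) adds that it produces weekly reports for the sessions. Under Section 8.6, logins are replaced only when the trial is complete, so access appears to last through all follow-ups.

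Controls carry on with their usual activities and receive the programme after the project ends. For follow-up, half of the groups complete the questionnaire online wherever they choose, and half are invited to the club. For intervention men who agree, "push notifications to complete the follow-up data can be sent from the smartphone app".

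**The concern.** The comparison of arms on money, time and days is fair only if both arms report these totals in the same way. After randomisation, one arm is given a dated record of money and time, from which days could be derived if every day is logged. The other arm is not described as having one. The Protocol neither tells men whether to use records nor asks whether they did.

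If recall misses spending, men who look it up report more for the same betting, and FFAB looks weaker. If recall overstates spending, FFAB looks stronger. At stake are RQ10 (whether FFAB has potential) and RQ11 (which outcomes a full trial should use). A measure could appear responsive or unresponsive partly because of the reporting aid. Section 5 also uses the 12-month data to assess progression.

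The Protocol already accepts that the conditions of data collection can affect answers, since it tests whether returning to the club biases responses. That experiment compares settings and does not address the diary.

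**Working it through.** **The plan's own figures.** Section 7.2.1: 4 clubs × 30 = 120 men, 60 per arm; 120 × 0.80 = 96 with follow-up data, or 48 per arm if losses are equal. These reproduce. The 95% confidence interval for a difference in means then has a half-width of about 1.96 × √(2/48) = 0.40 SD. The plan gives no figure for recall accuracy, diary accuracy or diary use at follow-up, so the bias cannot be computed from the documents.

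**Assumptions for illustration.**
- Recall reports a fraction ρ of the true amount.
- The diary reports all of it.
- A share s of intervention men consult the diary, and the rest recall as controls do.
- No control consults a record.

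Observed ratio = true ratio × (s/ρ + 1 − s).

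For a true 20% reduction (true ratio 0.80):

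| ρ | s | Calculation | Observed |
|---|---|---|---|
| 0.95 | 0.25 | 0.80 × (0.263 + 0.75) = 0.81 | 19% reduction |
| 0.8 | 0.5 | 0.80 × (0.625 + 0.5) = 0.90 | 10% reduction |
| 0.8 | 1 | 0.80 × (1.25 + 0) = 1.00 | no change |
| 0.7 | 0.75 | 0.80 × (1.071 + 0.25) = 1.06 | 6% increase |
| 1.2 | 0.5 | 0.80 × (0.417 + 0.5) = 0.73 | 27% reduction |

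**Relaxing the assumptions.** Let the diary report a fraction d of the truth, and let a share c of controls consult records of the same accuracy. Then

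observed ratio = true ratio × [s·d + (1 − s)ρ] / [c·d + (1 − c)ρ].

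- If d = ρ, or if c = s, the second factor is 1 and there is no bias.
- If men under-log (d = 0.7, ρ = 0.8, s = 0.5, c = 0): 0.80 × (0.35 + 0.40)/0.80 = 0.75, a 25% apparent reduction. The direction reverses compared with a complete diary at the same ρ and s.
- If some controls also look up records (d = 1, ρ = 0.8, s = 0.5, c = 0.25): 0.80 × (0.50 + 0.40)/(0.25 + 0.60) = 0.85, a 15% reduction instead of 10%.

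**Random error only.** If recall is right on average, the mean is not biased. With diary reliability 1, control reliability r and equal true variances, the standard error grows by √((1 + 1/r)/2): about 6% for r = 0.8 and 15% for r = 0.6.

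**Baseline adjustment.** Baseline is collected before randomisation, and so before the sessions teach the app. Adjustment handles differences between men at that point. It cannot handle a reporting aid that is added later in one arm.

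**The case against.** A reader might infer that the arms *are* measured with different accuracy, with controls answering from memory and intervention men from the diary. The documents do not support that. Nothing says how either arm answers. That controls lack the app is an inference from the description of the arms, though a strong one. Controls may also hold betting-account or bank records.

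Further objections have weight:

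- The validity statement in Section 4.2 suggests that recall and diary may agree well, which would put ρ near 1 and make the bias small. It gives no figure, and good agreement need not exclude a shift in the mean. It also does not address a trial in which only one arm keeps a diary.
- The diary is itself voluntary self-report, and Section 4.2 makes use of its data conditional on quality. Treating it as complete is an assumption.
- Sessions last nine weeks, so diary use has probably faded by 12 months, the primary time point.
- App engagement is logged (Sections 4.2, 5 and 8.6), so app use around each follow-up can be tabulated. This does not show whether a man consulted the diary to answer, and it says nothing about other records in either arm.
- Push notifications are optional and ask men to complete the questionnaire, which has a separate login. They bear more on who responds and when than on accuracy.
- Analyses are exploratory, and the interval of about ±0.40 SD is wide. Bias is still not reduced by a wide interval.

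It can also be said that questionnaire wording sits outside the Protocol. But whether a man consulted a record must be captured when he answers; no later analysis plan can recover it.

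**Conclusion.** The point holds as a possible difference in measurement between arms, not a demonstrated one. It applies to money and time, and to days only by derivation. Number of bets, breadth of gambling and the wellbeing measures are not listed as diary fields.

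Size and direction are unknown. In the five main illustrations, a true 20% reduction appears as anything between a 6% increase and a 27% reduction, with 19% in the mildest case. All of these rest on assumed values of ρ and s, a complete diary and no record use by controls. Bias in the mean needs systematic recall or logging error and unequal use of records. It is probably largest at 10 weeks and smaller at 12 months.

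A reader might also infer that the pilot would hide or inflate a real effect at its primary time point. The documents do not support going that far. They do show that the pilot, as written, would not reveal whether the problem exists, although helping to choose outcomes is one of its purposes.

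**What to change.** At baseline and at each follow-up, in the eCRF, paper and telephone versions:

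1. Give both arms the same neutral instruction on the use of records above the gambling questions.
2. Add one yes/no item after the block: *Did you look at any record (FFAB app, betting account, bank) to answer?*
3. Report the answers by arm and visit, beside the app-use logs already collected around each follow-up.
4. Take the result into account when judging responsiveness and choosing the primary outcome and follow-up method (RQ10 to RQ12).

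A comparison restricted to answers given without records should be exploratory only, and labelled as conditioning on behaviour after randomisation, because the men who look things up may differ between arms.

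A rule to answer only from memory is not recommended as the remedy. It may discard better answers, and it would not equalise the arms, since self-monitoring may itself improve recall.

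The cost is one instruction and one extra item per visit, fixed before data collection starts. The limitation is that this reveals the difference and does not fully remove it.

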8.5 Protocol compliance

The study team are aware that accidental protocol deviations can happen at any time. Such deviations will be documented using forms tailored to each activity within the research study and reported to the Chief Investigator and Sponsor immediately. Any deviations found to be occurring on a regular basis will initiate an emergency meeting of between the PI, the sponsor, representatives of the TSC and SSCs to consider appropriate action, including termination of the research study. Decision making processes will be documented and shared with the funder and ethics committee

The research team will collect all data using electronic data capture methods, ensuring that data collection activities are logged in encrypted server logs. This will provide a reference point for monitoring deviations from data collection protocols. The research team will also conduct observations of FFAB, which will provide opportunities to identify, report on and, where possible, correct protocol deviations.

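### App push prompts to complete follow-up can go to the intervention arm only, with no matching prompt for controls, so follow-up effort may differ by arm

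*Protocol*

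**What the plan says.** All of the following is in Protocol section 5, Phase 3, unless another place is given.

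- **Common follow-up.** Participants are followed up either online at a place of their choosing or at a club revisit. The first group gets "reminders sent via email, text and follow-up phone calls, if necessary". Men who do not attend a revisit are sent the link and then the same kind of reminders. A paper form is available to all. None of this depends on arm.
- **The arm-specific prompt.** The same part of the text adds: "For those receiving the intervention, and where they have agreed, push notifications to complete the follow-up data can be sent from the smartphone app".
- **Who has the app.** It is taught within the programme: "During sessions, men will learn to use the smartphone app to record time and money spent gambling". Under Control/Comparison group, "participants in the control arm will continue with their daily routines and usual activities", and they are offered the programme only after the project ends.
- **Last resort.** Where neither an online nor a paper response arrives, "a member of the research team will call participants and attempt to collect the data over the phone". This applies to both arms.
- **Nature and use of the data.** Outcomes are entirely self-reported. Of the electronic form the Protocol says: "This will be a confidential, self-completion method, which is optimal for collecting data on sensitive behaviours". The 12-month assessment is the primary time point and will be used to judge progression.
- **Contact with sessions.** Section 8.5 says: "The research team will also conduct observations of FFAB". Appendix 2 schedules observation in weeks 1 to 9 of Phase 3. The only masking mentioned is that of the statistician.

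**The concern.** A comparison of men who respond is cleanest when both arms are pursued equally. Here one reminder channel is tied to allocation, because only intervention men are taught the app during the trial. If the extra prompt brings in men who would otherwise not have replied, the responders in the two arms are no longer selected in the same way. The two response rates would also differ partly because of the procedure.

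Retention and completeness are among the results this pilot exists to report, and the 12-month outcomes feed the decision on a full trial. A procedure adopted here may also carry over into that trial, where random error would be smaller and the same imbalance would matter more.

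The Protocol already accepts that the way follow-up is collected can influence answers: it runs an experiment on whether returning to the club biases responses. It does not apply the same thought to a prompt sent from a component of the intervention.

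**Working it through.** **1. The plan's own figure.** Section 7.2.1: 4 clubs × 30 = 120 men, 120 / 2 = 60 per arm, and 120 × 0.80 = 96 men with follow-up data. This reproduces exactly, and equal retention gives 48 per arm. No figure in the Protocol is disputed.

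**2. How well the pilot could see a retention gap.** At 80% retention, the 95% half-width for the difference between arms is 1.96 × √(2 × 0.8 × 0.2 / 60) = 0.143, or 14.3 points. For one arm it is 1.96 × √(0.8 × 0.2 / 60) = 0.101, or 10.1 points.

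**3. Effect of a gap on the contrast.** Suppose there is no true effect and non-responders gamble d SD more than responders in both arms. With response rate r, the responder mean lies (1 − r) × d below the full mean. The intervention-minus-control contrast among responders then shifts by

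(1 − r_c) × d − (1 − r_i) × d = (r_i − r_c) × d.

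The Protocol gives neither d nor the gap. Both are assumed below, with the gap centred on 80%. Power is for a two-sided 5% test of the gap with 60 per arm.

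| Assumed gap | Responders of 60, control v intervention | Power to detect gap | Shift, d = 0.25 | d = 0.5 | d = 1.0 |
|---|---|---|---|---|---|
| 5 points | 46.5 v 49.5 | 10% | 0.0125 | 0.025 | 0.05 |
| 10 points | 45 v 51 | 28% | 0.025 | 0.05 | 0.10 |
| 15 points | 43.5 v 52.5 | 54% | 0.0375 | 0.075 | 0.15 |

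**4. Against random error.** With 48 per arm and no baseline adjustment, the half-width for a mean difference is 1.96 × √(2 / 48) = 0.40 SD. Every shift in the table is well below that.

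**5. Direction.** On the assumption in step 3, the shift is towards more gambling in the intervention arm, so FFAB looks worse. If non-responders gambled less, the sign would reverse. A separate hypothetical runs the other way. If 10 to 30% of intervention data came by phone and were shaded downward by 0.2 to 0.5 SD in that arm only, the contrast would move by 0.1 × 0.2 = 0.02 to 0.3 × 0.5 = 0.15 SD in FFAB's favour. The Protocol supplies none of these inputs, so it does not settle the net sign.

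**The case against.** The push prompt is optional and needs the man's agreement. It sits on top of a sequence of reminders that does not depend on arm and ends with a phone call to every remaining non-responder, which should narrow any early gap. The effect estimates are labelled exploratory and adjusted for baseline. All of this stands, and it limits the point to one avoidable difference in effort.

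A reader might infer more than the text supports:

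- **That unequal response is built in.** Only unequal effort is permitted. Whether response differs depends on how many men agree and react, and the Protocol gives no basis for estimating that.
- **That a 5 to 15 point retention artefact is to be expected.** That range is an input to the illustration, not a result. The Protocol also does not say that retention will be reported by arm.
- **That the comparison of follow-up methods (RQ12) is distorted.** That experiment compares online with club-revisit completion. Nothing ties mode to arm, and push could be used under either mode.
- **That the fallback calls are unmasked.** The Protocol says that research team members make the calls and that the team observes sessions. It does not say that callers observed sessions or see allocation. The possibility is left open, not stated. Participants themselves cannot be masked, so some self-report bias would remain whatever callers know.

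**Conclusion.** The point holds in a narrow form. The Protocol allows one prompt for outcome data in the intervention arm only and names no counterpart for controls. On assumed gaps of 5 to 15 points and differences of 0.25 to 0.5 SD, the bias would be about 0.01 to 0.075 SD, rising to 0.15 SD if non-responders differ by a full SD. This is small beside the pilot's random error of about 0.40 SD.

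The pilot would probably not reveal the cause afterwards: even a 15 point gap would be detected only about half the time. Prevention is therefore better than later adjustment, although the result of the pilot is unlikely to turn on it. This is a matter of trial conduct, and a statistical analysis plan could describe the imbalance but not equalise the contacts.

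**What to change.** In section 5, Phase 3, Methods for data collection:

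1. Whenever a push prompt for outcome data is sent, send control men a matched text at the same time. Alternatively, keep push for programme use and do not use it for outcome collection.
2. State that reminder dates and channels are otherwise identical in both arms.
3. Log mode of completion (online, club, paper, phone) and number of contacts, and tabulate both by arm.
4. As a secondary precaution, because the Protocol does not exclude callers who observed sessions, have existing staff who neither observed nor supported sessions make the fallback calls from a fixed script where feasible.

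The cost is a few extra texts or the loss of one optional channel, some reallocation of calls among existing staff, and two logged fields. With a small team, full separation of callers may not always be possible, which is why the fourth item is worded as a precaution.
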